Patients with neuropsychological diagnoses are reported to be more likely to develop severe COVID-19 disease. Previous work has shown an increased incidence of severe respiratory infection and worse critical care outcomes associated with pharmacological neuropsychological treatments. It remains unclear whether particular conditions or treatments predispose to severe COVID-19 disease (requiring hospital, critical care admission or death) more than to other acute respiratory infections. Patients with COVID-19 disease are reported to subsequently have a high incidence of neuropsychological disease. However, the incidence of neuropsychological sequelae is also high following other critical illness. It is unclear whether neuropsychological sequelae following severe COVID-19 disease are more serious or managed differently than following other severe acute respiratory infection (SARI) such as bacterial or viral pneumonia, particularly when accounting for risk factors associated with the disease.

Antecedent analysis

We will explore the associations between pharmacological treatments (hypnotics and anxiolytic, antidepressant, drugs used in psychoses and related disorders) of preexisting neuropsychological diagnoses (anxiety, mood, psychotic disorders, or dementia), and severe clinical outcomes of COVID-19 infection (hospital admission, ICU admission and death) in comparison to those not receiving such treatments.

We will determine whether the associations between pre-existing neuropsychological treatments and severe clinical outcomes differ for patients with COVID-19 infection in comparison to patients with non-COVID-19 severe acute respiratory infections (SARI)

Sequelae analysis

We will determine the risks of receiving a new neuropsychological diagnosis or new neuropsychological medication within one year after discharge from hospital for patients admitted with COVID-19 infection in comparison to patients with non-COVID-19 severe acute respiratory infections (SARI) investigating the subgroups of hospitalised patients admitted to and not admitted to an ICU.

INTRODUCTION

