This study will investigate neuropsychological disease and treatments before and after severe COVID-19 disease. The two main aims are:

1. to evaluate the associations of pre-existing neuropsychological diseases and treatments with severe COVID-19 outcomes in comparison to patients without pre-existing neuropsychological pathology;

2. to evaluate the associations between hospital or ICU admission due to COVID-19 and neuropsychological sequelae following discharge home in comparison to patients with ICU admission due to non-COVID-19 severe acute respiratory infections (SARI).

Objectives

- 1. To assess whether pre-existing neuropsychological diseases (by separate diseases and overall) are associated with severe COVID-19 outcomes (hospital and ICU admission and death) in comparison to the general population.
- 2. To assess whether pre-existing neuropsychological treatments (as a class and individually where possible) are associated with severe COVID-19 outcomes (hospital and ICU admission and death) and whether these explain disease associations in comparison to those not receiving such treatments.
- 3. To assess whether the risk of severe COVID-19 outcomes with prior neuropsychological disease differs from the risk of severe outcomes with SARI.

After discharge following a hospital admission for COVID -19 infection:

- 4. To assess the incidence of new neuropsychological diseases up to one year after hospital and ICU discharge following treatment for COVID-19 disease.
- 5. To compare the incidence of new neuropsychological diseases up to one year after hospital and ICU discharge with COVID-19 disease to the incidence following discharge after treatment for SARI.

Summary of the potential impact

This study will provide a better understanding of how pre-existing psychopathology and concomitant medication affect the risk of hospital and ICU admission and death due to COVID-19 and how any differences between those with and without preexisting psychopathology and COVID-19 infection compare to other severe acute respiratory infections. We will discover the neuropsychological sequelae of admission to a hospital or ICU with COVID -19 disease, taking into account prior neuropsychological disease and whether these differ from patients discharged from an ICU following SARI. These findings will be key to prevention and management of ongoing problems for these patients.

METHODS

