Royston Parmar flexible parametric survival models will be used to estimate the hazard ratio of severe COVID-19 outcome (hospital or critical care admission and death) in cohort 1 for patients with neuropsychological disease at study entry compared with those without disease, and for individual neuropsychological diseases and treatments.

This analysis will be adjusted for the listed covariates. The age variable will be included as a restricted cubic spline rather than a linear term. Before commencing analysis, we will assess the numbers of patients with each comorbidity, and may if necessary group the presence of certain less common comorbidities together. Any such grouping will be done on the basis of clinical similarities only and prior to examining any outcomes by comorbidity. We may also include a time-varying binary covariate to record any new diagnosis and/or treatment which occurs after study entry in patients originally free from both diagnosis and treatment, depending on the number of these events. Proportional hazards assumptions will be tested, and time dependent terms will be included if the hazard ratio changes over time (I.e. if the association between neuropsychological disease and risk of severe COVID-19 has changed during the course of the pandemic). A random frailty term will be included to account for similarities amongst patients registered in the same primary care practice. Possible interactions between exposure and age, sex and ethnicity will be considered and tested using a Wald test.

The same methods will be used for secondary analyses in which the main exposure variable will be defined as either the presence of a specific class of neuropsychological disorder or any other neuropsychological disorders or no disorder.

The primary analysis will be used to estimate the hazard ratio of severe SARI outcomes in cohort 2 using the same exposure variables.

If non-proportional hazards are observed in either cohorts 1 or 2, then maximum follow-up time will be capped at 1 year and a time-dependent covariate will be added to the analysis of both cohorts to maintain the comparability of results.

Aim 2.

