Sensitivity analyses

We will undertake complete case analysis in those without missing data as a sensitivity analysis of our findings.

We will also restrict analysis to only include patients with confirmed COVID-19 diagnosis using RNA testing.

For Aim 2 we will carry out a sensitivity analysis in cohort four with additional censoring of follow-up on 24th January 2020, so that outcomes are assessed prior to the pandemic period. In comparing cohort 3 and 4 we will consider the competing risk of death by undertaking a competing risk analysis.

In order to compensate for the low expected event rates relative to our sample sizes for aim 2, we will combine cohorts 3 and 4 and use all available baseline characteristics (as listed previously) to calculate a propensity score to measure the likelihood of developing a new neuropsychological condition up to 1 year after ICU admission. We will then use these scores (with inverse probability weighting) to compare the adjusted hazard of developing a new neuropsychological condition in patients admitted to critical care for COVID compared to those admitted for SARI.

The authors will have full access to anonymised data from the Case Mix Programme, QResearch and Public Health England, and Hospital Episode statistics databases. We will remove duplicate records for the same individual, and set dates and values outside a pre-defined credible range as missing. For patients admitted with SARI between 2015-2020 the full set of standard data validation processes for unit level data intended for public reporting will have been carried out by ICNARC. Some of the more recent Covid admissions will have undergone a more restricted set of validations, but these do include confirming the total number of admission with Covid to each unit, checking that duration of organ support does not exceed duration of stay, and confirming with units that that aggregated units level summaries of length of stay and organ support (among other measures) are in line with expectations. All variables used in the analysis will be initially summarised in a table of baseline characteristics to include minimum, maximum, median and quartiles.

Data linkage

Person-level data linkage will be undertaken between QResearch, Hospital Episode Statistics, the Case Mix Programme and Public Health England. Cases will be matched on pseudonymised NHS number [15].

Discussion

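### Objective 3 asks whether the association differs between COVID-19 and SARI, but the Aim 1 methods name only a separate hazard ratio per cohort and no contrast, interval or test for the difference

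*Protocol*

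**What the plan says.** Objective 3 reads: "To assess whether the risk of severe COVID-19 outcomes with prior neuropsychological disease differs from the risk of severe outcomes with SARI". The summary, under Antecedent analysis, makes the same commitment for treatments: "We will determine whether the associations between pre-existing neuropsychological treatments and severe clinical outcomes differ for patients with COVID-19 infection", the comparison being with SARI patients.

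Statistical Methods, Aim 1, sets out the analysis:

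- For cohort 1: "Royston Parmar flexible parametric survival models will be used to estimate the hazard ratio of severe COVID-19 outcome".
- For cohort 2: "The primary analysis will be used to estimate the hazard ratio of severe SARI outcomes in cohort 2 using the same exposure variables".
- For effect modification: "Possible interactions between exposure and age, sex and ethnicity will be considered and tested using a Wald test". Cohort, or type of infection, is not among the modifiers.
- If non-proportional hazards appear in either cohort, follow-up is capped at one year in the analysis of both, and a "time-dependent covariate will be added to the analysis of both cohorts to maintain the comparability of results".

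The Sensitivity analyses section adds nothing for this question. The pooling described there belongs to Aim 2: "we will combine cohorts 3 and 4 and use all available baseline characteristics".

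**The concern.** The target of objective 3 is a difference between two associations. The stated analysis ends with one association per cohort. Whether each hazard ratio differs from 1 says nothing direct about whether they differ from each other, and whether two intervals overlap is not a 5% test of their difference.

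At stake is the conclusion that prior neuropsychological disease or its treatment matters more, less or equally in COVID-19 than in other respiratory infection. The comparison is of interest for disease overall, four disease classes and three treatment classes. With no named contrast, the verdict for each would be left to judgement after the results are seen.

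**Working it through.** **Step 1. Match each between-infection question to its analysis.**

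| Question | Analysis stated | Contrast of COVID-19 with SARI named? |
|---|---|---|
| Objective 3 (prior disease, severe outcome) | One model in cohort 1, the same model in cohort 2 | No |
| Summary, same question for treatments | As above | No |
| Objective 5 (new disease after discharge) | One model comparing cohort 3 with cohort 4 | Yes, a hazard ratio |

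The protocol therefore specifies a direct contrast for objective 5 and none for objective 3. The conditional one-year cap makes the two Aim 1 models more alike, but it does not compare them.

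**Step 2. Look for a figure to reproduce.** There is none. For Aim 1 the protocol gives about 8.3 million adults, but no event count, effect size or precision. Every input in steps 3 and 4 is an assumption chosen for illustration.

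**Step 3. Compute the missing quantity on assumed inputs.** Let HR1 (COVID-19) and HR2 (SARI) have log-scale standard errors s1 and s2, and let their log estimates have correlation rho.

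- Ratio of hazard ratios: RHR = HR1 / HR2
- SE(log RHR) = sqrt(s1² + s2² − 2·rho·s1·s2)
- 95% interval: exp(log RHR ± 1.96·SE)

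Take HR1 = 1.50 and HR2 = 1.40, so log RHR = ln(1.50/1.40) = 0.069 and RHR = 1.07. For s1 = s2 = 0.02 and rho = 0, SE = sqrt(0.0004 + 0.0004) = 0.0283 and z = 0.069/0.0283 = 2.44.

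| SE of each log HR | rho | 95% CI, HR1 | 95% CI, HR2 | Overlap? | RHR (95% CI) | p |
|---|---|---|---|---|---|---|
| 0.01 | 0 | 1.47–1.53 | 1.37–1.43 | No | 1.07 (1.04–1.10) | <0.001 |
| 0.02 | 0 | 1.44–1.56 | 1.35–1.46 | Yes | 1.07 (1.01–1.13) | 0.015 |
| 0.02 | 0.2 | 1.44–1.56 | 1.35–1.46 | Yes | 1.07 (1.02–1.13) | 0.006 |
| 0.04 | 0 | 1.39–1.62 | 1.29–1.51 | Yes | 1.07 (0.96–1.20) | 0.22 |

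Rows two and four look alike side by side: both hazard ratios are above 1 and their intervals overlap. They give different answers on the difference.

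**Step 4. The general reason.** With equal standard errors and independence, two 95% intervals just touch when the log hazard ratios are 2 × 1.96 = 3.92 SE apart. A 5% test needs only 1.96 × sqrt(2) = 2.77 SE. Intervals that just touch correspond to z = 3.92/sqrt(2) = 2.77, p = 0.006.

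**Step 5. Are the two estimates comparable and independent?**

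- *Shared people.* Cohort 1 requires registration by 24 January 2019. Cohort 2 is open to adults registered for at least a year between January 2015 and January 2020. Many people, and the same practices, can contribute to both. Risk periods do not overlap, because cohort 2 is censored when cohort 1 starts. The documents do not allow the covariance to be sized.
- *Death.* Cohort 1 counts death from any cause after COVID-19 infection. The outcome definition for cohort 2 lists death without qualification, although the cohort description censors at death from other causes.
- *Follow-up.* Cohort 1 runs from 24 January 2020 to 30 June 2021, about 17 months. Cohort 2 can run for up to five years. They are aligned only if non-proportional hazards are found.

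**The case against.** The strongest reply is that this is detail a statistical analysis plan can supply. The protocol states the question, cohorts, outcomes and model, and it plainly intends the two results to be compared, since it takes care to keep them comparable. That part stands: nothing in the Aim 1 methods is wrong in itself. It does not dispose of the point. The section goes down to the age spline, the frailty level, named interactions, a Wald test and the number of imputations, and it gives objective 5 its contrast while leaving objective 3 without one.

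Several stronger readings are tempting, and the documents do not support them:

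- *A reader might infer that the plan cannot yield an estimate of the difference.* It can. Two fitted models give two log hazard ratios with standard errors, from which the ratio follows. The contrast is unspecified, not unobtainable.
- *A reader might infer that the plan will judge by overlapping intervals or paired significance.* It states no such rule.
- *A reader might infer that shared people make the estimates materially dependent.* The risk periods are disjoint and the outcomes differ, so the covariance may be small.
- *A reader might infer from 8.3 million adults that every hazard ratio will be significant.* No event counts are given, some outcomes are rarer than others, and the Bias section expects some conditions to be protective.

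It is also fair that overlapping intervals coexist with p < 0.05 only in a band, from z = 1.96 to 2.77 with equal standard errors. The table shows cases inside and outside it.

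**Conclusion.** The point holds in a limited form. A numbered objective and a commitment in the summary ask for a difference between associations, and the stated Aim 1 analysis names no contrast, interval or test for it. The finding rests on reading the text, not on the arithmetic. The numerical example uses assumed hazard ratios, standard errors and correlation, and shows only that side-by-side hazard ratios can mislead about the difference; it does not predict this study's results. The size of any effect on the conclusions, including the effect of shared people on the variance, cannot be determined from the protocol. The change is worth making before analysis because it is cheap and the objective is otherwise left open to post hoc judgement.

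**What to change.** Add to Statistical Methods, Aim 1, that objective 3 will be answered by the ratio of hazard ratios, COVID-19 versus SARI, with a 95% confidence interval, for neuropsychological disease overall and for the disease and treatment classes. State how it is obtained: either from the two fitted models by the formula above, or from a stacked model of cohorts 1 and 2 with a cohort-by-exposure interaction. The stacked form is not essential. With a separate baseline hazard and separate covariate effects per cohort, it essentially reproduces the two fits and mainly adds the covariance.

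Because people and practices can appear in both cohorts, use a variance that allows for this, for example a cluster-robust one, or show as a check that the covariance is negligible.

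Before the ratio is interpreted, define the death component the same way in both cohorts as far as the data allow, and fix a common follow-up length in advance rather than only if non-proportional hazards appear.

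No new data are needed. Taking the ratio from the two fits costs a few sentences and a short calculation per exposure. A stacked or cluster-robust fit costs more computing, given about 8.3 million adults in Aim 1 and five imputed datasets. Aligning death and follow-up means editing the outcome definitions and may mean refitting both models.

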A retrospective cohort data linkage study of patients aged 18 years and above registered in English general practices. This protocol is written following RECORD guidance [12].

Settings Describe the setting, locations, and relevant dates, including periods of recruitment, exposure, follow-up, and data collection.

1205 general practices in England contributing to the QResearch database, which is nationally representative. We defined cohorts during the COVID pandemic as between 24th January 2020 (the date of the first confirmed COVID-19 case in England) and study end (30th June 2021). We defined retrospective comparison cohorts as the 5 years prior to this date (24th January 2015- 23rd January 2020).

Data linkage

The study will include adult patients registered with the QResearch database. Practices must have been contributing to the QResearch database for at least 12 months. For the investigation of associations of pre-existing neuropsychological diseases and treatments (cohort 1) patients must be registered for at least a 12-month period before 24th January 2020. For the investigation of incidence of new neuropsychological diseases (cohort 2) patients must be registered for at least a 12-month period between January 2015 to 2020. The date of study entry is separately defined below for each study cohort.

Patients in QResearch will be linked to: (1) the ICNARC Case Mix Programme (CMP) database, the national clinical database from adult critical care; (2) the Hospital Episode Statistics (HES) data warehouse containing records of all patients admitted to NHS hospitals and Emergency departments in England; (3) the national registry of COVID-19 RT-PCR positive test results from Public Health England (PHE); and (4) Office of National Statistics COVID-19 mortality data, which includes all deaths due to COVID-19 in England. Data linkage will be based primarily on NHS number. For a description of the datasets see Supplemental material S1.

Participants

Give the eligibility criteria, and the sources and methods of selection of participants. Describe methods of follow-up. The methods of study population selection (such as codes or algorithms used to identify subjects) should be listed in detail.

Aim 1.

From the linked dataset, we will extract two cohorts to explore the association between neuropsychological diseases and treatments and hospitalisation, ICU admission or death:

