 Cohort one is adult patients aged 18 years of age or over on 24th January 2020 (the study entry date, when the first confirmed COVID-19 case occurred in the UK) who were registered in a primary care practice within the QResearch programme on or before 24th January 2019. Patients will be followed-up from study entry date until development of severe COVID-19 disease, defined as the first date of either hospitalisation, ICU admission, or death. Patients will be censored at the first occurrence of deregistration from the GP practise, death, or date of the final data extract from the linked datasets.

Cohort two is an open cohort of patients aged 18 years of age or over (including those who become 18 within this period) who had been registered with a primary care practise within the QResearch database for at least one year, between 24th January 2015 and 23rd January 2020. For each patient, the earliest day on which all these conditions were met will be defined as their study entry date, and they will be followed-up until development of severe disease due to SARI, defined as hospitalization, ICU admission, or death. Patients will be censored at the earliest of first occurrence of deregistration from the GP practise, death from other causes, 24th January 2020 or date of the final data extract from the linked datasets.

Aim 2.

- Cohort three will include adult patients (aged 18+ on date of hospital admission) discharged alive following a hospital admission including an ICU admission resulting from COVID -19 infection (defined below) between 24 January 2020 and study end date, who were registered in a primary care practice within the QResearch programme before their ICU admission. It will be used to evaluate the risk of subsequent neuropsychological sequalae from the date of discharge. Patients will be censored at the earliest of first occurrence of deregistration from the GP practice, death from other causes, 12 months post discharge from hospital, or date of the final data extract from the linked datasets.

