For aim 1, the various different neuropsychological conditions of patients in cohort 1 are likely to result in varying levels of exposure to covid-19, compared to the populations without these conditions, with some conditions likely to have a protective effect, but in other conditions the reverse is expected. We have added a secondary analysis to examine the effect of specific conditions in order to evaluate this.

For aim 2, the two cohorts have experienced their exposure of interest (ICU admission with either COVID or SARI) during different time frames. Patients with SARI (admitted to ICU between 2015 to 2020) will have longer follow-up, but patients with COVID (admitted to ICU during 2020/21) may have benefited from the recently increasing public awareness of mental health conditions. To combat this, we have capped all follow-up at a maximum of 1 year post ICU discharge, and we will include a time-dependent covariate to assess whether risk varies with time post discharge. We have also included a cohort of patients with SARI admitted during 2020/21 for comparison with the COVID cohort during the same time frame.

We will derive the E-value to estimate the extent unmeasured confounding.

Study Size

For aim 1 we will use the entire QResearch database of approx. 8.3 million adult patients to maximise precision and minimise selection bias. We chose to use the last 5 years of ICNARC data for SARI comparisons to use recent data whilst having sufficient numbers for comparison taking into account the numbers from previous studies and after linkage [13, 14].

For aim 2, we will use all known ICU admissions from the ICNARC database for SARI and/or COVID who can be linked to the QResearch database. In cohort 3 the expected sample size is in the region of 11,000 admissions in total, for cohort 4 it is likely to be in the region of 7,000 admissions per year, and for cohort 5 around 3,500 patients.

Quantitative variables

Quantitative variables will be treated as continuous variables without categorisation. Descriptive summary statistics (mean and standard deviation, median interquartile range or number (%) as appropriate) will be used to present sociodemographic and clinical characteristics of patients with and without COVID-19 infection for those with and without neuropsychiatric conditions or treatments.

Statistical Methods

Aim 1.

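### Aim 1 caps follow-up at one year only if non-proportional hazards are seen, so a test result sets the horizon and cuts off the last five months of the pandemic window

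*Protocol*

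**What the plan says.** Statistical Methods, Aim 1, responds to non-proportional hazards in two places.

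- In the paragraph on the cohort 1 model: "Proportional hazards assumptions will be tested, and time dependent terms will be included if the hazard ratio changes over time". The explanation given is that this applies "if the association between neuropsychological disease and risk of severe COVID-19 has changed during the course of the pandemic". No truncation is mentioned there.
- At the end of the Aim 1 text: "If non-proportional hazards are observed in either cohorts 1 or 2, then maximum follow-up time will be capped at 1 year". The companion step and its purpose follow in that sentence: "a time-dependent covariate will be added to the analysis of both cohorts to maintain the comparability of results".

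Settings places the pandemic cohorts "between 24th January 2020 (the date of the first confirmed COVID-19 case in England) and study end (30th June 2021". Under Participants, cohort 1 has a single start for everyone: "24th January 2020 (the study entry date, when the first confirmed COVID-19 case occurred in the UK". Cohort 2 is an open cohort running from 24 January 2015 to 23 January 2020. Study Size gives the reason for its length: "We chose to use the last 5 years of ICNARC data for SARI comparisons to use recent data whilst having sufficient numbers for comparison".

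Sensitivity analyses lists no uncapped version of Aim 1. For Aim 2, by contrast, the Bias section applies a one-year limit unconditionally.

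**The concern.** In cohort 1, time since entry and calendar time are the same thing. A hazard ratio that varies with time since entry is therefore one that varied over the pandemic, which is what the time-dependent terms are meant to describe. Under the second rule, finding such variation removes the final part of the period in which it would be described. Because the trigger is non-proportionality in either cohort, a time-varying association in the 2015 to 2020 SARI data would also remove COVID-19 data from 2021, even if the COVID-19 hazards were proportional.

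Two things are at stake. The quantity reported as the main Aim 1 result would cover either about 17 months or 12 months of the pandemic, depending on what the data show. And the SARI comparator could lose most of its follow-up, although five years were chosen for recency and numbers.

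**Working it through.** The protocol gives no event count or power figure for Aim 1, so there is no stated figure to reproduce. The check is date arithmetic, followed by two illustrations on stated assumptions.

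**Cohort 1** (entry date from Participants, study end from Settings)
- 24 January 2020 to 30 June 2021 = 523 days, or 523 / 30.4375 = 17.2 months.
- A one-year cap runs to 24 January 2021 = 366 days, since 2020 is a leap year.
- Lost: 523 − 366 = 157 days, or 5.2 months; 157 / 523 = 30.0%. Counting the cap as 365 days gives 158 days (30.2%).
- This assumes that the final data extract reaches 30 June 2021.

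**Cohort 2, one patient present throughout**
- 24 January 2015 to 24 January 2020 = 1,826 days. Kept: 365. Lost: 1,461 / 1,826 = 80.0%.

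**Cohort 2, whole open cohort** (turnover is not given, so it is assumed)
- Take a steady state in which exits at annual rate q are replaced by entries. Per place in the cohort, total person-time is 5 years.
- Capped person-time is 1 + 4(1 − e^−q), so the share lost is 1 − [1 + 4(1 − e^−q)] / 5 = 0.8·e^−q.
- The share of kept person-time from patients already eligible at the start (hence from January 2015 to January 2016) is [(1 − e^−q)/q] / [1 + 4(1 − e^−q)].

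| Assumed turnover per year | Person-time lost | Kept person-time from patients eligible at the start |
|---|---|---|
| 0% | 80% | 100% |
| 5% | 76% | 82% |
| 10% | 72% | 69% |
| 20% | 66% | 53% |

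- Extreme case, uniform entry over five years and no exits: mean follow-up is 2.5 years and mean capped follow-up is (4 × 1 + 0.5) / 5 = 0.9 years, so the loss is 1 − 0.9 / 2.5 = 64%. Nobody is present at the start in this case, so the tilt to the earliest year does not apply.

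**How easily the cap could be triggered** (all inputs assumed)
- Split D events equally between an early and a late period, with a share p in exposed patients. The standard error of the difference in log hazard ratios is √[2 / (D/2 · p(1 − p))].
- Hazard ratio moving from 1.50 to 1.40, p = 25%: ln(1.50/1.40) = 0.069. With D = 40,000 the standard error is √[2(1/5,000 + 1/15,000)] = 0.0231 and z = 2.99. Scaling by √D gives z of about 1.5 at 10,000 events, 2.1 at 20,000 and 4.7 at 100,000.
- Ratio of hazard ratios 1.10, p = 20%, two-sided 5%: the chance of a significant result is 48% at 10,000 events, 77% at 20,000 and 99% at 50,000.

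**The case against.** The cap has a stated purpose, comparability of the two cohorts, and equal maximum follow-up serves it in part. It also keeps follow-up close to the date at which exposure was measured. The cap comes with a time-dependent covariate, so change over the first 12 months can still be estimated. No listed objective asks for an association in early 2021. All of this stands, and it defeats the reading that the cap blocks Objective 3: a one-year contrast remains.

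A reader might also infer that, with some 8.3 million adults, any trivial drift is bound to trigger the cap. The document does not support that. Power depends on events, which are not given, and at 10,000 events the drift illustrated above would not reach significance. The method of judging non-proportionality may properly sit in an analysis plan that is not at hand, so the lack of a threshold is not the criticism here.

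A third tempting inference is that, if the cap is not triggered, exposure status drifts more over five years than over 17 months and biases the comparison towards COVID-19. The protocol gives nothing from which to size this. It allows an optional time-varying covariate for new diagnosis or treatment in patients initially free of both. Drift large enough to matter would also tend to appear as non-proportional hazards. This remains an unquantified possibility and is not part of the finding.

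The objection does not answer why comparability should depend on a test result. A common horizon can be fixed in advance, as it is for Aim 2, and time-dependent terms deal with non-proportional hazards without truncation.

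**Conclusion.** The point holds in a limited form. The protocol lets an observed result decide the follow-up horizon of the main Aim 1 analysis, and either cohort can trigger the change. If triggered, the cap removes 157 to 158 of 523 days (30%) in cohort 1. That figure is firm, given an extract to 30 June 2021. In cohort 2 it removes 80% for a patient present throughout, and about 64% to 80% of person-time overall under the assumed entry and exit patterns. With steady turnover of 5% to 20% a year, 53% to 82% of what is kept comes from the earliest year, which sits badly with choosing five years for recent data and sufficient numbers. That tilt depends on most patients being eligible at the start.

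The consequence is a restricted pandemic-trend analysis and an estimand that depends on the data. Objective 3 can still be addressed. How likely the trigger is cannot be stated from the document; the illustrations show only that a modest change could suffice if events are numerous.

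**What to change.** Delete the conditional cap from Statistical Methods, Aim 1. In its place:

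1. Keep follow-up to 30 June 2021 in cohort 1, and all of cohort 2, as the main analysis. Use time-dependent terms where needed, and report hazard ratios at prespecified times or pandemic periods.
2. For the COVID-19 versus SARI comparison in Objective 3, prespecify a common one-year horizon in both cohorts, reported whatever the proportional-hazards assessment shows.

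The cost is a change of wording and one additional analysis per cohort, on data already extracted. Dividing cohort 2 into successive yearly periods with exposure and covariates re-read at each start is an optional refinement. It would use all five SARI years at a one-year horizon, but needs a new entry rule, repeated derivation of variables and errors clustered by patient, so the correction should not depend on it.
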